2.1.5.1 Lifestyle Requirements

1. For 2-3 days following each cleaning visit subjects must discontinue all regular oral hygiene practices (products and procedures) and use only the study fluoride-free toothpaste and toothbrush provided, twice daily, with the exception of interdental cleaners, e.g., dental floss, if this is their normal practice.
2. For the 21 days of each treatment period, subjects may use only the study product assigned to them and the provided toothbrush twice daily, after breakfast and just before going to bed. Subjects may floss if this is their normal practice.
3. Subjects must wear their lower partial denture 24 hours a day, except when cleaning it, during each 21-day treatment period. Subjects will be encouraged to remove their mandibular partial denture at night during the washout and lead in periods.
4. Subjects may use a non-zinc fixative like Poligrip® on their upper denture but no adhesive is permitted in the lower partial denture.
5. Subjects must refrain from eating canned sardines during the course of the study and may not eat hard candy or nuts when the specimens are in place.

2.1.6 Discontinuation Criteria

Discontinued subjects are those who do not complete final evaluations and/or procedures outlined in the protocol because of one of the following:

- a) an AE;
- b) significant protocol deviation that, in the opinion of the Investigator, may compromise the study results;
- c) voluntary withdrawal; or
- d) withdrawal at the Investigator's discretion.

The Investigator/Sponsor may recommend dropping a subject from the study at any time. Recommendations to drop a subject may include but are not limited to: misuse of study product, not following study procedures, or a serious protocol violation. Any subject who is discontinued from the study that has a continuing AE will have follow-up communications about the AE until the AE is resolved to the satisfaction of the Investigator/Medical Monitor.

2.1.7 Product Accountability

Study products will be stored in a secure area, under environmental condition as required by label instructions or as described in this protocol and dispensed only under the authorization of the Investigator. The storage condition shall be properly documented. The study site will record and log both the receipt and dispensation of all test products (used and unused) by using forms provided by the

Sponsor or suitable forms provided by the site. Study products will be returned to the Sponsor following the trial, or alternatively, they will be destroyed at the clinical site provided the site has an existing SOP for the destruction of clinical materials and prior written approval from the Sponsor.

2.1.8 Treatment Codes

The site will be provided with a code breaker report in a sealed envelope (except for Period 5). The sealed code breaker report contains documents that list the kit box number or treatment code while the identity of the treatment products is hidden by an opaque scratch-off seal. If the study blind needs to be broken, an individual subject's investigational product may be ascertained by opening the sealed code breaker report, locating the subject's kit box number or treatment code and scratching off the opaque seal to reveal the treatment identity. The sealed code breaker report will be opened if a clinically Serious Adverse Event (SAE) occurs or management of the subject requires knowledge of the identity of the investigational product. The Investigator should immediately inform the Sponsor that the code will be broken and record the date, time and reason for breaking the code in writing. After the study is complete and the study database has been finalized and locked, treatment codes will be unblinded.

2.1.9 Source Data

The Investigator has the responsibility for ensuring that all source documents (i.e., study and/or medical records) and CRFs are completed and maintained according to the study protocol and is available at the site. Any CRF used as a source document must be identified as such in the Investigator Notebook.

2.2 SELECTION AND WITHDRAWAL OF STUDY POPULATION

2.2.1 Inclusion Criteria

In order to be included in the study, each subject must:

- i. Be between 18 and 85 years of age;
- ii. Provide written informed consent prior to participation and be given a signed copy of the informed consent form;
- iii. Be in general good health as determined by the Investigator based on a review of the health history/update for participation in the trial;
- iv. Be wearing a removable mandibular partial denture with sufficient room in one posterior buccal flange area to accommodate two 4 mm round enamel specimens and room on the same side to accommodate two 4 mm round specimens in the buccal surface of two posterior denture teeth;
- v. Be willing and capable of wearing their removable partial denture 24 hours a day for four (4), three-week treatment periods;
- vi. Be willing to allow study personnel to drill specimen sites (as described in #iv) in their mandibular partial denture;
- vii. Be in good medical and dental health with no active caries or periodontal disease (NOTE: subjects presenting at screening with caries may continue in the study if their carious lesions are restored prior to beginning treatment 1);
- viii. Have a salivary flow rate in the range of normal values (unstimulated whole saliva flow rate \geq 0.2 mL/min; gum base stimulated whole saliva flow rate \geq 0.8 mL/min).

2.2.2 Exclusion Criteria

Subjects may be excluded from study participation due to:

- i. Currently being pregnant, intending to become pregnant during the study period, or breast feeding;
- ii. Currently having any medical condition that could be expected to interfere with the subject's safety during the study period;

- iii. Currently taking antibiotics or having taken antibiotics in the two weeks prior to beginning treatment 1;
- iv. Having participated in another clinical study or receipt of an investigational drug within 30 days of beginning treatment 1; or
- v. Taking fluoride supplements, required to use a fluoride mouthrinse, or have received a professional fluoride treatment in the two weeks preceding specimen placement;
- vi. Currently taking or have ever taken bisphosphonate drugs (e.g., Fosamax, Actonel and Boniva) for the treatment of osteoporosis.

2.2.3 Continuance Criteria

Subjects may be excluded from study participation and/or the analysis due to:

- i. Use of any non-study oral hygiene products since the previous study visit;
- ii. Having any diseases or condition that might interfere with the safe participation in the study;
- iii. Having an inability to undergo study procedures;
- iv. Significant protocol deviation that, in the opinion of the Investigator, may compromise the study results;
- v. Use of antibiotics since the previous study visit;
- vi. Being unwilling or incapable of wearing their removable partial denture 24 hours a day for a fifth, three-week treatment period (asked at Period 5, Visit 22 only).

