2.1.2 Design Type

This is a randomized, four-treatment, 4-period crossover, double blind clinical trial. The target population is approximately 16 adult volunteers. During the course of the study, all subjects will be asked to voluntarily participate in a fifth period, not included as part of the crossover design. Those subjects willing to participate in Period 5 will sign an amended informed consent form and will all receive the same product during that period. Two to three days before the start of each treatment period the subjects will have their teeth cleaned to remove all accessible plaque and calculus and will be provided with a non-fluoride dentifrice to use until their next visit. At the beginning of each testing period, two gauze-covered 4 mm round partially demineralized human enamel specimens will be placed in the buccal flange area of the subject's mandibular partial denture. In addition, two gauze-covered 4 mm round partially demineralized human enamel specimens will be placed in the buccal surface of two posterior denture teeth of the same side of the partial denture. Once specimens are placed, subjects will wear their partial dentures twenty-four hours a day and use their assigned toothpaste twice daily, as instructed, until their next visit. Subjects will return at 7 and 14 days to have one specimen removed per visit, and again at 21 days to have the remaining two specimens removed. The specimen removal sequence will occur in a predetermined order starting with the anterior denture tooth specimen, posterior denture tooth specimen, and then the two buccal flange specimens. Following the 21-day specimen removal visit, the subjects will undergo a four- to five-day washout period followed by another cleaning and two- to three-day lead in period. This process will be repeated until all subjects have used all four test products. Changes in the mineral content of the enamel specimens will be assessed using the SMH. Enamel fluoride uptake (EFU) will be determined using the microdrill enamel biopsy technique.

Table 1. Study Schedule by Procedure Type and Visit

PROCEDURE	VISIT 1	VISIT 2, 7, 12, 17, 22	VISIT 3, 8, 13, 18, 23	VISIT 4, 9, 14, 19, 24	VISIT 5, 10, 15, 20, 25	VISIT 6, 11, 16, 21, 26
	SCREENING	PROPHY	BEGIN TREATMENT	7 DAY REMOVAL	14 DAY REMOVAL	END ¹ TREATMENT
Informed Consent	X					
Medical History Review	X	X	X	X	X	X
Demographics	X					
Oral Soft Tissue Exam	X	X	X			X
Oral Hard Tissue Exam	X	X (v2 only)				X (v21 and v26)

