Salivary Flow	X					
Inclusion/Exclusion Criteria	X					
Continuance Criteria		X	X	X	X	X
Randomization			X (v3 only)			
Dental Prophylaxis		X				
Placement of specimens			X			
Issue washout toothpaste		X				
Return washout toothpaste			X			

Issue study products and diary			X			
Return study products and diary						X
General Comments	X	X	X	X	X	X
Adverse Events		X	X	X	X	X
Subject Accountability						X ¹ (v21 or 26)

¹ For those subjects continuing on Period 5, end of study activities will occur at Visit 26

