2.1.5 Duration of Subject Participation

Visit 1 (Screening)

Subjects who have been recruited for the study via a telephone interview will sign in at the study site for this and all subsequent visits. At this time, subjects will be asked to read and sign duplicate copies of an informed consent statement, authorization for the release of health information for research form and demographic form. Demographic information and study entry criteria will be obtained and documented on the appropriate case report form (CRF). Upon review of these documents, an update of their medical

history/medications and the inclusion/exclusion criteria, each subject will be given an oral soft/hard tissue exam (OSHT) prior to their acceptance into the study. Their mandibular partial denture will be examined to determine if specimens can be held in one buccal flange area and the posterior denture teeth of the same side, as previously described. They will then provide a stimulated and unstimulated saliva sample to determine salivary flow rate. If no contraindications to their participation are discovered and the subject meets the study requirements, the subject will be accepted into the study.

General comments, if any, will be recorded on the appropriate CRF.

Visit 2 (Prophy Period 1)

Two to three days prior to the beginning of Treatment Period 1, subjects will return for a professional dental prophylaxis. Subjects will answer have their medical history/medication information updated and answer continuation questions. Subjects will then receive an oral soft tissue exam (OST) and oral hard tissue exam (at the first period only). The subject's mandibular partial denture will be prepared to hold the round enamel specimens by drilling out hollows in the partial dentures at the specimen sites in the buccal flange area and the buccal surface of two denture teeth on the same side of the partial denture. A temporary dental material (DentuSil™) will be placed in the drilled-out areas of the partial denture. Subjects will be given fluoride-free toothpaste to use at home for the next two to three days until they return for their next visit. They will be encouraged to remove their partial denture at night until their next visit.

Visit 3 (Begin Treatment Period 1)

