Each subject will receive an OST examination, answer continuation questions and have their medical history/medication information updated. Subjects will be asked to return the washout product they received at Visit 2 and will be given their randomized study product and diary for product use. Subjects will be instructed on the brushing method (see Appendix). The four enamel partially demineralized specimens will be placed in the buccal flange/posterior teeth areas on one side of the subject's mandibular partial denture. All subjects will be instructed to wear their partial denture containing the enamel specimens 24 hours a day except during the cleaning of their natural teeth (twice per day) and for short periods to rinse their mouth out with tap water after meals and snacks.

Visit 4 (7 Day Removal)

Seven (7) days following Visit 3, the subjects will return to the Institute and answer continuance criteria questions and update their medical history/medication information. One enamel specimen will be removed from anterior denture tooth site of their partial denture and the hollow will be filled with a temporary dental material (DentuSil™). The subjects will be told to continue using their assigned product as instructed.

Visit 5 (14 Day Removal)

Fourteen (14) days following Visit 3, the subjects will return to the Institute and answer continuance criteria questions and update their medical history/medication information. One enamel specimen will be removed from posterior denture tooth site of their partial denture and the hollow will be filled with a temporary dental material (DentuSil™). The subjects will be told to continue using their assigned product as instructed.

Visit 6 (End Treatment Period 1)

Twenty-one (21) days following Visit 3, the subjects will return to the Institute and receive an OST examination, answer continuance criteria questions and update their medical history/medication information. Subjects will be asked to return the study product and diary they received at Visit 3. The remaining two enamel specimens in the buccal flange site will be removed from their partial denture and the hollows will be filled with a temporary dental material (DentuSil)

Period 2, 3, 4 & 5

The procedures outlined above (Visit 2-6) will be repeated until each subject has used each of the four test products, followed by a 5th test product in Period 5. At Visit 21 (and also at Visit 26 for those subjects

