3.1.4 Treatment Compliance

Product use compliance will be assessed by determining the average weight of each type of test product prior to dispensing (five tubes per product will be weighed and average weight determined). At the end of each treatment period, subjects will be required to return all product containers (including empty ones) to the study site. The tubes will be individually weighed upon return and that number subtracted from the average weight will be recorded on the treatment dispensing log.

The amount of test product used for each study treatment will be compared to daily product usage recorded on the subject's diary. Significant discrepancies will be discussed with the study subject, as needed. Subjects who miss 15% or more treatments within the three-week treatment period will be considered non-compliant. The reason for non-compliance will be noted in the subjects' study records. All subjects will be instructed to use only the assigned products in place of normal oral hygiene for the duration of the study.

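### Minor, wrong as written: no visit is scheduled to issue paste for the 4-5 day washouts, although using one's own paste then meets a continuance criterion; and the subject sheet gives two weeks for a 21-day wear period

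*Combined protocol and SAP*

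**What the plan says.** **Washout and paste.** Section 2.1.2 says that after the Day-21 visit "the subjects will undergo a four- to five-day washout period followed by another cleaning and two- to three-day lead in period". At that visit, according to Section 2.1.5 (Visit 6), "Subjects will be asked to return the study product and diary they received at Visit 3"; no paste is handed out. The fluoride-free paste comes at the cleaning visit (Section 2.1.5, Visit 2): "Subjects will be given fluoride-free toothpaste to use at home for the next two to three days until they return for their next visit". Table 1 agrees. Its row "Issue washout toothpaste" is marked under the cleaning visits (2, 7, 12, 17, 22) and not under the end-of-treatment visits.

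**Product rules.** Section 2.1.5.1 sets two windows. Item 1 begins "For 2-3 days following each cleaning visit subjects must discontinue all regular oral hygiene practices", and item 2 begins "For the 21 days of each treatment period, subjects may use only the study product assigned to them". Section 3.1.4 is broader: subjects are to "use only the assigned products in place of normal oral hygiene for the duration of the study". The Appendix allows only products given to the subject unless staff say otherwise. Section 3.1.1 and the washout instructions in the Appendix both assume that the subject has a washout toothpaste. Section 2.2.3(i) then lists "Use of any non-study oral hygiene products since the previous study visit" as a ground for possible exclusion, with no exemption for any interval. Table 1 schedules the continuance check at every visit from Visit 2 on.

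**Wear period.** Section 2.1.5.1 item 3 requires 24-hour wear throughout each 21-day treatment period, and Section 2.2.1(v) says three weeks. The subject sheet in the Appendix states the same rule for a two-week period.

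**The concern.** A subject in the washout has been told to use a supplied paste, holds none under the schedule, and at the next visit is asked whether anything else was used. Followed literally, the choices are not to brush with toothpaste, to obtain a staff permission that no section provides for in advance, or to use one's own paste and so meet an exclusion ground. With 16 subjects randomized so that at least 10 complete, and no replacement (Sections 5.4.1 and 2.2.4), an exclusion route triggered by ordinary conduct should not be left in the text.

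The wear error matters because of which specimens are in the mouth in the third week. A subject who took the sheet at its word would regard the 24-hour rule as ended at Day 14, when the only specimens left are those read at Day 21 for the primary endpoint.

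**Working it through.** The plan has no figure of its own to reproduce on the washout, and the sample size was set on logistical grounds (Section 5.3). The check is of the schedule, with calendar arithmetic.

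**Paste held between periods** (Sections 2.1.2 and 2.1.5, Table 1)

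| Step | Visits | Paste in the subject's hands afterwards |
|---|---|---|
| End of treatment, Day 21 | 6, 11, 16 (21 before Period 5) | Test paste returned, none issued |
| Washout, 4-5 days | none | None scheduled |
| Cleaning | 7, 12, 17 (22) | Fluoride-free paste issued |
| Lead-in, 2-3 days | none | Fluoride-free paste |
| Begin treatment | 8, 13, 18 (23) | Fluoride-free paste returned, test paste issued |

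**Days not covered**
- Crossover: 3 washouts x 4 days = 12, to 3 x 5 = 15 days per subject.
- With Period 5, assuming the same washout precedes it: 4 x 4 = 16, to 4 x 5 = 20 days.
- Days between periods: 4 + 2 = 6, to 5 + 3 = 8. Uncovered share: lowest 4/(4 + 3) = 57%, highest 5/(5 + 2) = 71%.

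**Where the criterion applies.** At Visits 7, 12, 17 and 22 the preceding visit is the Day-21 visit, so the interval that 2.2.3(i) looks back over is exactly the uncovered washout.
- Crossover checks: Visits 2 to 21 = 20, of which Visits 7, 12 and 17 = 3, so 3/20 = 15%.
- With Period 5: Visits 2 to 26 = 25 checks, 4 of them after a washout, so 4/25 = 16%.

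These ratios locate the fault; they do not predict exclusions. Visit 2 has the same wording problem, since it looks back to screening, but it precedes randomization at Visit 3 and touches no analysis set.

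**Link to the analysis.** Section 2.2.3 says that exclusion can extend to the analysis. Section 5.4.1 defines ITT as subjects randomized and exposed at least once. Section 5.4.2 removes subjects with major protocol deviations from PP. Neither mentions criterion (i).

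**Wear period.** Two weeks = 14 days against 21, a shortfall of 7 days. Four specimens are placed; one comes out at Day 7 and one at Day 14, leaving 4 - 2 = 2 in the flange for Day 21. Section 2.1.1 names Day-21 enamel fluoride uptake as the primary endpoint.

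**The case against.** The strongest reply is that the sponsor plainly meant to cover the washout: Section 3.1.1 has a paragraph on a washout product, and the Appendix tells subjects to use the one provided. That is right about intent, and it rules out saying that the plan intends subjects to have no paste. But neither place gives an issue time, and the paste that Table 1 calls washout paste is handed out only after the 4-5 days have passed. What remains is a fault of timing in the schedule.

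It can also be said that staff may authorize other products (Appendix) and that exclusion is only permitted, not required. Both stand and keep the point minor. A staff permission does not, however, alter 2.2.3(i) or 3.1.4.

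A reader might infer more than the text supports:
- *That usual products are allowed in the washout because 2.1.5.1 is silent.* Sections 3.1.1 and 3.1.4 and the Appendix all point the other way.
- *That the investigator decides under criterion (i).* Section 2.2.3 names no decision-maker for it; only item (iv) mentions the investigator.
- *That subjects will drop out of the analysis.* Section 5.4 does not apply the criterion explicitly.
- *That washout fluoride biases the 0 versus 2800 ppm comparison.* Each period starts with a cleaning, a fluoride-free lead-in and new specimens, and the documents show no such effect.

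On wear, the diary in the same Appendix runs to Day 21, and the 24-hour rule is also given in person at Visit 3. The Visit 5 reminder concerns product use, not wear. These make lost wear unlikely but do not correct the sheet.

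**Conclusion.** Both faults are in the text, and both are minor. First, no paste is scheduled for 12-15 days per subject in the crossover (16-20 with Period 5), while the product rules assume one is held and 2.2.3(i) counts any other product as a discretionary ground for exclusion. The day counts rest on the stated 4-5 day washout and on Table 1 read together with the visit descriptions. How many subjects would use their own paste, and whether any would be excluded, cannot be estimated from the documents. Second, the subject sheet understates the 24-hour wear period by 7 days, in the week when only the Day-21 specimens remain. No bias in fluoride uptake and no loss of wear is shown, and the safeguards already in the design make a material effect unlikely. Sample size, alpha and the primary analysis are untouched.

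**What to change.** 1. Issue the fluoride-free paste at the Day-21 visits 6, 11 and 16, and at 21 for those continuing to Period 5. Keep the Visit 2 issue for Period 1. Amend the Visit 6 description and the Table 1 issue row to match.
2. Extend Section 2.1.5.1 item 1 to cover the washout as well as the lead-in.
3. Limit 2.2.3(i) to intervals in which study or fluoride-free paste has been issued. This also cures Visit 2.
4. In the Appendix, replace the two-week wording of the wear rule with 21-day, and reissue the subject sheet.

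Allowing usual products in the washout instead would be the weaker choice, because it contradicts 3.1.1, 3.1.4 and the Appendix. The cost is 4-5 more days of fluoride-free paste per gap, a few lines of protocol text and a corrected sheet. No visits are added, since subjects already attend at both ends of each washout.
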